5.3 Duration of Therapy

In the absence of treatment delays due to adverse event(s), treatment may continue until one of the following criteria applies:

- Disease progression
 - With the caveat that patients who show evidence of clinical benefit may be permitted to continue atezolizumab treatment after disease progression, if they meet the criteria outlined in Section [11.4](#).
- Intercurrent illness that prevents further administration of treatment
- Unacceptable adverse event(s)
- Patient decides to withdraw from the study
- General or specific changes in the patient's condition render the patient unacceptable for further treatment in the judgment of the investigator
- Patient non-compliance
- Pregnancy
 - All women of childbearing potential should be instructed to contact the investigator immediately if they suspect they might be pregnant (e.g., missed or late menstrual period) at any time during study participation.
 - The investigator must immediately notify CTEP in the event of a confirmed pregnancy in a patient participating in the study.
- Termination of the study by sponsor
- The drug manufacturer can no longer provide the study agent

The reason(s) for protocol therapy discontinuation, the reason(s) for study removal, and the corresponding dates must be documented in the Case Report Form (CRF).

5.4 Duration of Follow-Up

Patients will be followed for 90 days after the last dose of atezolizumab is administered or until the patient enrolls on another protocol or death, whichever comes first. Follow-up will consist of three telephone calls from the Study Team: one call between Day 27 and Day 30 after the last dose of atezolizumab, one call between Day 57 and Day 60 after the last dose, and one call between Day 87 and Day 90 after the last dose. Patients removed from study for unacceptable adverse event(s) will be followed until resolution or stabilization of the adverse event.

5.5 Criteria for Removal from Treatment and/or Study

Patients will be removed from study for one of the following reasons: completed 30-day follow-up period, toxicities are unresolved but stabilized, patient enrolls on another protocol, patient receives other type of treatment-intent therapy, pregnancy, or death. The reason for study removal and the date the patient was removed must be recorded on the case report form.

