NOTE: Protocol specific exceptions to expedited reporting of serious adverse events are found in the Specific Protocol Exceptions to Expedited Reporting (SPEER) portion of the CAEPR.

Expedited AE reporting timelines are defined as:

- "24-Hour; 5 Calendar Days" - The AE must initially be submitted electronically within 24 hours of learning of the AE, followed by a complete expedited report within 5 calendar days of the initial 24-hour report.
- "10 Calendar Days" - A complete expedited report on the AE must be submitted electronically within 10 calendar days of learning of the AE.

¹Serious adverse events that occur more than 30 days after the last administration of investigational agent/intervention and have an attribution of possible, probable, or definite require reporting as follows:

Expedited 24-hour notification followed by complete report within 5 calendar days for:

- All Grade 3, 4, and Grade 5 AEs

Expedited 10 calendar day reports for:

- Grade 2 AEs resulting in hospitalization or prolongation of hospitalization

²For studies using PET or SPECT IND agents, the AE reporting period is limited to 10 radioactive half-lives, rounded UP to the nearest whole day, after the agent/intervention was last administered. Footnote "1" above applies after this reporting period.

Effective Date: May 5, 2011

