7.3.5 Adverse Events of Special Interest in Atezolizumab Studies

The following AEs are considered of special interest (AESIs) in patients receiving atezolizumab and must be reported expeditiously through CTEP-AERS, irrespective of regulatory seriousness criteria:

Drug-Specific AESIs

- Systemic lupus erythematosus
- Nephritis
- Ocular toxicities (*e.g.*, uveitis, retinitis)
- Grade ≥2 cardiac disorders (*e.g.*, atrial fibrillation, myocarditis, pericarditis)
- Events suggestive of hypersensitivity, infusion-related reactions, cytokine release syndrome, macrophage activating syndrome and hemophagocytic lymphohistiocytosis.
- Vasculitis
- Autoimmune hemolytic anemia
- Severe cutaneous reactions (*e.g.*, Stevens-Johnson syndrome, dermatitis bullous, toxic epidermal necrolysis)

Non Drug-Specific AESIs

- Cases of potential drug-induced liver injury that include an elevated ALT or AST in combination with either an elevated bilirubin or clinical jaundice, as defined by Hy's Law and based on the following observations:
 - Treatment-emergent ALT or AST > 3 x ULN (or > 3 x baseline value in disease states where LFTs may be elevated at baseline) in combination with total bilirubin > 2 x ULN (of which ≥ 35% is direct bilirubin)
 - Treatment-emergent ALT or AST > 3 x ULN (or > 3 x baseline value in disease states where LFTs may be elevated at baseline) in combination with clinical jaundice

- Suspected transmission of an infectious agent by the study treatment, as defined below:
 - Any organism, virus, or infectious particle (e.g., prion protein transmitting transmissible spongiform encephalopathy), pathogenic or non-pathogenic, is considered an infectious agent. A transmission of an infectious agent may be suspected from clinical symptoms or laboratory findings that indicate an infection in a patient exposed to a medicinal product. This term applies only when a contamination of study treatment is suspected.

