7.4 Routine Adverse Event Reporting

All Adverse Events **must** be reported in routine study data submissions. **AEs reported expeditiously through CTEP-AERS must also be reported in routine study data submissions.**

Adverse event data collection and reporting, which are required as part of every clinical trial, are done to ensure the safety of patients enrolled in the studies as well as those who will enroll in future studies using similar agents. AEs are reported in a routine manner at scheduled times during the trial using Medidata Rave. For this trial the Adverse Event CRF is used for routine AE reporting in Rave.

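### Section 5.5 takes patients off study after a 30-day follow-up period, while Section 5.4 requires 90 days and three dated calls

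*Combined protocol and SAP*

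**What the plan says.** Section 5.4 (Duration of Follow-Up) states: "Patients will be followed for 90 days after the last dose of atezolizumab is administered". Enrollment on another protocol or death ends this follow-up sooner. It consists of three telephone calls. The first falls at Days 27-30. The second is given as "one call between Day 57 and Day 60 after the last dose", while the third is set out as "one call between Day 87 and Day 90 after the last dose". Anyone taken off for unacceptable toxicity is followed until the event resolves or is stable.

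Section 5.5 (Criteria for Removal from Treatment and/or Study), which follows directly, lists the reasons for removing a patient from study. The first is a "completed 30-day follow-up period". Others include death, enrollment on another protocol, and "patient receives other type of treatment-intent therapy". The reason and date of removal go on the case report form.

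**The concern.** The two sections give different lengths for the same follow-up, and the protocol has no rule on which prevails. Removal under Section 5.5 is worded as something that will happen, not as an option. In a multicenter trial, similar patients could therefore be followed for different times and given different off-study dates.

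What is at stake is active safety follow-up after treatment. Section 2.3.4.1 gives a terminal half-life of 27 days, so exposure continues well past Day 30. The protocol's other post-treatment limits also run longer: 10 weeks for immunostimulatory agents and 100 days for live vaccines (Section 5.2), and 150 days for pregnancy reporting (Section 7.5). An adverse event in Days 31-90 can be reported only if the site learns of it, and the second and third calls are the contacts scheduled for that purpose.

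**Working it through.** The plan states no figure to reproduce. The check sets the two sections side by side and counts the calls that would be lost.

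**Inputs**
- Section 5.4: follow-up of 90 days from the last dose; call windows at Days 27-30, 57-60 and 87-90.
- Section 5.5: removal after 30 days, with no start point given.
- Section 10: 21-day cycles, with a new cycle delayed by up to 2 weeks for scheduling.
- Section 6.1: toxicity holds of up to 84 days beyond the scheduled infusion.

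**Is Section 5.4 consistent with itself?** Yes. The three windows are about 30 days apart and the last closes on Day 90.

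**Is a 30-day follow-up period defined elsewhere?** No. The 30-day limit in Section 7.3.3 governs expedited adverse event reporting, not how long a patient is followed.

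**Calls lost.** Let the 30 days start A days after the last dose, so that removal falls on Day A + 30. Count a call as lost if its window opens after that day.

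| Start of the 30 days | Removal day | Calls lost |
|---|---|---|
| Last dose (A = 0) | 30 | 2 (windows open on Days 57 and 87) |
| A below 27 | before 57 | 2 |
| A from 27 to 56 | 57 to 86 | 1 |
| A of 57 or more | 87 or later | 0 |

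With the last-dose anchor, follow-up is 90 - 30 = 60 days shorter than Section 5.4 requires (60/90 = 67%), and 2 of 3 calls are omitted.

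**Is a later start plausible?** Yes. If a patient stops at the restaging that closes a cycle, the decision comes about 21 days after the last dose, or 21 + 14 = 35 days if the next cycle has been delayed by two weeks. Counted from that decision, two calls are lost at A = 21 and one at A = 35.

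**Toxicity holds.** A held patient may stay on study until 21 + 84 = 105 days after the last dose before discontinuation is required. Section 5.5 then removes nothing in Days 31-90.

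**Drug remaining, by simple half-life decay.** 2^(-30/27) = 0.46 at Day 30 and 2^(-90/27) = 0.10 at Day 90.

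**After correction.** With removal at Day 90 from the last dose, all three windows close on or before the removal day and no call is lost.

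**The case against.** The best reply is that sites will follow Section 5.4. It is the section devoted to length of follow-up and it gives dated windows, whereas Section 5.5 is only a list of removal reasons. Ninety days is evidently what was meant, and many sites will read it so. That makes the correction uncontroversial, but it leaves a wrong removal criterion in force.

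Three further objections limit the point, and they stand.
- The count of two lost calls depends on the last-dose anchor, which Section 5.5 does not state.
- Patients on a toxicity hold, or followed for the adverse event that took them off, remain under observation regardless of the 30 days.
- Patients who die, enroll on another protocol or start other treatment-intent therapy leave study under Section 5.5 in any case.

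A reader might infer that late adverse events would go unreported. The text does not support this. Section 7.4 says that "AEs are reported in a routine manner at scheduled times during the trial using Medidata Rave" and sets no 30-day limit. Section 7.3.3 provides that serious events more than 30 days after the last dose that "have an attribution of possible, probable, or definite require reporting as follows". Events of special interest "must be reported expeditiously through CTEP-AERS, irrespective of regulatory seriousness criteria" (Section 7.3.5). The study calendar also marks an off-treatment adverse event evaluation. The duty to report survives; what is at risk is the scheduled contact that would bring an event to light.

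**Conclusion.** The inconsistency is real and minor. If the 30 days run from the last dose, a site applying Section 5.5 omits the Day 57-60 and Day 87-90 calls. It loses the scheduled contacts in Days 31-90 for patients who are neither on a toxicity hold nor being followed for an unresolved adverse event. The two stated lengths conflict whatever the anchor, but the number of calls lost does not stay at two.

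Two stronger readings should be resisted. One is to multiply the lost calls by planned enrollment to get a trial-wide total. That would assume that every site applies Section 5.5, that every patient would otherwise have reached Day 90, and that the anchor is the last dose; the documents establish none of these. The other is that deaths would be missed as progression-free survival events. Section 11.2.6 does count death as an event, and for a patient who stops without progression a death in Days 31-90 could in principle go unobserved. However, the documents give no rate for such deaths. Section 11.3 also asks for response assessments to continue until progression is unequivocal, and Section 11.2.4.3 asks for efforts to document progression after discontinuation in patients with symptomatic deterioration. Any effect on this secondary endpoint therefore cannot be quantified. The primary response rate and the Simon rules in Section 13.1 do not depend on the post-treatment calls.

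**What to change.** In Section 5.5, replace 30-day with 90-day and state that the period runs from the last dose of atezolizumab. The anchor needs stating because 90 days counted from a later point, such as the decision to stop, would overrun the Section 5.4 schedule and leave the two sections in disagreement. The cost is a short wording amendment. It adds no call, visit or scan beyond those Section 5.4 already requires.

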6. DOSING DELAYS/DOSE MODIFICATIONS

6.1 General AE Management and Dose Modification Guidelines

There will be no dose reduction for atezolizumab in this study.

Patients may temporarily suspend study treatment for up to 84 days (12 weeks) beyond the scheduled date of delayed infusion if study drug-related toxicity requiring dose suspension is experienced. If atezolizumab is held because of AEs for >84 days beyond the scheduled date of infusion, the patient will be discontinued from atezolizumab and will be followed for safety and efficacy as specified in this protocol. If the AE resolves within 84 days and the patient is receiving corticosteroid therapy for the event, atezolizumab may be held for longer than 84 days (up to 4 weeks) in order to allow tapering of the steroid dose to ≤ 10 mg oral prednisone or equivalent.

Dose interruptions for reasons other than toxicity, such as surgical procedures, may be allowed. The acceptable length of interruption will be at the discretion of the study PI in consultation with CTEP.

The primary approach to grade 1 to 2 irAEs is supportive and symptomatic care with continued treatment with atezolizumab; for higher-grade irAEs, atezolizumab should be withheld and oral and/or parenteral steroids administered. Recurrent grade 2 irAEs may also mandate withholding atezolizumab or the use of steroids. Assessment of the benefit risk balance should be made by the investigator, with consideration of the totality of information as it pertains to the nature of the toxicity and the degree of clinical benefit a given patient may be experiencing prior to further administration of atezolizumab. Atezolizumab should be permanently discontinued in patients with life threatening irAEs.

6.2 Management of Specific AEs

Management of certain AEs of concern, including immune-related pneumonitis, hepatitis, colitis, endocrinopathies, pancreatitis, neuropathies, meningoencephalitis, and potential ocular toxicities are presented in the Atezolizumab Investigator's Brochure. See the **Agent Administration Guidelines** in this document, including the “**Administration of First and Subsequent Atezolizumab Infusions**” table for guidelines for the management of Infusion Related Reactions and Anaphylaxis.

Atezolizumab has been associated with risks such as the following: IRRs and immune-related hepatitis, pneumonitis, colitis, pancreatitis, diabetes mellitus, hypothyroidism, hyperthyroidism, adrenal insufficiency, hypophysitis, Guillain-Barré syndrome, myasthenic syndrome or myasthenia gravis, meningoencephalitis, myocarditis, nephritis, myositis, and severe cutaneous adverse reactions. Immune-mediated reactions may involve any organ system and may lead to hemophagocytic lymphohistiocytosis and macrophage activation syndrome.

[Use the following paragraph in studies enrolling patients with lung cancer. Studies not enrolling lung cancer patients may delete.] Pleural and pericardial effusion

Patients experiencing dyspnea, chest pain, or unexplained tachycardia should be evaluated for the presence of a pericardial effusion. Patients with pre-existing pericardial effusion should be followed closely for pericardial fluid volume measurements and impact on cardiac function. When intervention is required for pericardial or pleural effusions, atezolizumab should be held, and appropriate workup includes cytology, lactate dehydrogenase (LDH), glucose, cholesterol, protein concentrations (with pleural effusions), and cell count.

Pulmonary events

Dyspnea, cough, fatigue, hypoxia, pneumonitis, and pulmonary infiltrates have been associated with the administration of atezolizumab. Patients will be assessed for pulmonary signs and symptoms throughout the study and will have computed tomography (CT) scans of the chest performed at every tumor assessment.

All pulmonary events should be thoroughly evaluated for other commonly reported etiologies such as pneumonia or other infection, lymphangitic carcinomatosis, pulmonary embolism, heart failure, chronic obstructive pulmonary disease, or pulmonary hypertension. Management guidelines for pulmonary events are provided in the table below.

Event	Management
Pulmonary event, Grade 1	
 Continue atezolizumab and monitor closely. Re-evaluate on serial imaging. Consider patient referral to pulmonary specialist.
Pulmonary event, Grade 2	
 Withhold atezolizumab for up to 12 weeks after event onset.^a

Event	Management
	
 ● Refer patient to pulmonary and infectious disease specialists and consider bronchoscopy or BAL. ● Initiate treatment with corticosteroids equivalent to 1–2 mg/kg/day oral prednisone. ● If event resolves to Grade 1 or better, resume atezolizumab.^b ● If event does not resolve to Grade 1 or better while withholding atezolizumab, permanently discontinue atezolizumab. ● For recurrent events, treat as a Grade 3 or 4 event.
Pulmonary event, Grade 3 or 4	
 ● Permanently discontinue atezolizumab. ● Bronchoscopy or BAL is recommended. ● Initiate treatment with corticosteroids equivalent to 1–2 mg/kg/day oral prednisone. ● If event does not improve within 48 hours after initiating corticosteroids, consider adding an immunosuppressive agent. ● If event resolves to Grade 1 or better, taper corticosteroids over ≥1 month.

BAL = bronchoscopic alveolar lavage

^a Atezolizumab may be withheld for a longer period of time (*i.e.*, >12 weeks after event onset) to allow for corticosteroids (if initiated) to be reduced to the equivalent of ≤10 mg/day oral prednisone. The acceptable length of the extended period of time must be determined by the investigator and the Medical Monitor.

^b If corticosteroids have been initiated, they must be tapered over ≥1 month to the equivalent of ≤10 mg/day oral prednisone before atezolizumab can be resumed.

Hepatic events

Immune-mediated hepatitis has been associated with the administration of atezolizumab. Eligible patients must have adequate liver function, as manifested by measurements of total bilirubin and hepatic transaminases, and liver function will be monitored throughout study treatment. Management guidelines for hepatic events are provided in the table below.

Patients with right upper-quadrant abdominal pain and/or unexplained nausea or vomiting should have liver function tests (LFTs) performed immediately and reviewed before administration of the next dose of study drug.

For patients with elevated LFTs, concurrent medication, viral hepatitis, and toxic or neoplastic etiologies should be considered and addressed, as appropriate.

Event	Management
Hepatic event, Grade 1	
 ● Continue atezolizumab.

Event	Management
	
 • Monitor LFTs until values resolve to within normal limits or to baseline values.
Hepatic event, Grade 2	
All events:
 
 • Monitor LFTs more frequently until return to baseline values. 
Events of >5 days' duration:
 
 • Withhold atezolizumab for up to 12 weeks after event onset.^a • Initiate treatment with corticosteroids equivalent to 1–2 mg/kg/day oral prednisone. • If event resolves to Grade 1 or better, resume atezolizumab.^b • If event does not resolve to Grade 1 or better while withholding atezolizumab, permanently discontinue atezolizumab.
Hepatic event, Grade 3 or 4	
 • Permanently discontinue atezolizumab. • Consider patient referral to gastrointestinal specialist for evaluation and liver biopsy to establish etiology of hepatic injury. • Initiate treatment with corticosteroids equivalent to 1–2 mg/kg/day oral prednisone. • If event does not improve within 48 hours after initiating corticosteroids, consider adding an immunosuppressive agent. • If event resolves to Grade 1 or better, taper corticosteroids over ≥1 month.

LFT = liver function test.

^a Atezolizumab may be withheld for a longer period of time (*i.e.*, >12 weeks after event onset) to allow for corticosteroids (if initiated) to be reduced to the equivalent of ≤10 mg/day oral prednisone. The acceptable length of the extended period of time must be determined by the investigator.

^b If corticosteroids have been initiated, they must be tapered over ≥1 month to the equivalent of ≤10 mg/day oral prednisone before atezolizumab can be resumed.

Gastrointestinal events

Immune-mediated colitis has been associated with the administration of atezolizumab. Management guidelines for diarrhea or colitis are provided in the table below.

All events of diarrhea or colitis should be thoroughly evaluated for other more common etiologies. For events of significant duration or magnitude or associated with signs of systemic inflammation or acute-phase reactants (*e.g.*, increased C-reactive protein, platelet count, or bandemia): Perform sigmoidoscopy (or colonoscopy, if appropriate) with colonic biopsy, with three to five specimens for standard paraffin block to check for inflammation and lymphocytic infiltrates to confirm colitis diagnosis.

Event	Management
Diarrhea or colitis, Grade 1	
 • Continue atezolizumab. • Initiate symptomatic treatment. • Endoscopy is recommended if symptoms persist for >7 days.

Event	Management
	
 • Monitor closely.
Diarrhea or colitis, Grade 2	
 • Withhold atezolizumab for up to 12 weeks after event onset.^a • Initiate symptomatic treatment. • Patient referral to GI specialist is recommended. • For recurrent events or events that persist >5 days, initiate treatment with corticosteroids equivalent to 1–2 mg/kg/day oral prednisone. • If event resolves to Grade 1 or better, resume atezolizumab.^b • If event does not resolve to Grade 1 or better while withholding atezolizumab, permanently discontinue atezolizumab.
Diarrhea or colitis, Grade 3	
 • Withhold atezolizumab for up to 12 weeks after event onset.^a • Refer patient to GI specialist for evaluation and confirmatory biopsy. • Initiate treatment with corticosteroids equivalent to 1–2 mg/kg/day IV methylprednisolone and convert to 1–2 mg/kg/day oral prednisone or equivalent upon improvement. • If event resolves to Grade 1 or better, resume atezolizumab.^b • If event does not resolve to Grade 1 or better while withholding atezolizumab, permanently discontinue atezolizumab.
Diarrhea or colitis, Grade 4	
 • Permanently discontinue atezolizumab. • Refer patient to GI specialist for evaluation and confirmation biopsy. • Initiate treatment with corticosteroids equivalent to 1–2 mg/kg/day IV methylprednisolone and convert to 1–2 mg/kg/day oral prednisone or equivalent upon improvement. • If event does not improve within 48 hours after initiating corticosteroids, consider adding an immunosuppressive agent. • If event resolves to Grade 1 or better, taper corticosteroids over ≥1 month.

GI = gastrointestinal.

^a Atezolizumab may be withheld for a longer period of time (*i.e.*, >12 weeks after event onset) to allow for corticosteroids (if initiated) to be reduced to the equivalent of ≤10 mg/day oral prednisone. The acceptable length of the extended period of time must be determined by the investigator.

^b If corticosteroids have been initiated, they must be tapered over ≥1 month to the equivalent of ≤10 mg/day oral prednisone before atezolizumab can be resumed.

Endocrine disorders

Thyroid disorders, adrenal insufficiency, diabetes mellitus, and pituitary disorders have been associated with the administration of atezolizumab. Management guidelines for endocrine events are provided in the table below.

Patients experiencing one or more unexplained AEs possibly indicative of endocrine dysfunction (including headache, fatigue, myalgias, impotence, mental status changes, and constipation) should be investigated for the presence of thyroid, pituitary, or adrenal endocrinopathies. The patient should be referred to an endocrinologist if an endocrinopathy is suspected. Thyroid

stimulating hormone (TSH) and free T3 and T4 levels should be measured to determine whether thyroid abnormalities are present. Pituitary hormone levels and function tests [e.g., TSH, growth hormone, luteinizing hormone, follicle-stimulating hormone, testosterone, prolactin, adrenocorticotrophic hormone (ACTH) levels, and ACTH stimulation test] and MRI of the brain (with detailed pituitary sections) may help to differentiate primary pituitary insufficiency from primary adrenal insufficiency. The table below describes dose management guidelines for hyperthyroidism, hypothyroidism, symptomatic adrenal insufficiency, and hyperglycemia.

Event	Management
Asymptomatic hypothyroidism	
 • Continue atezolizumab. • Initiate treatment with thyroid replacement hormone. • Monitor TSH weekly.
Symptomatic hypothyroidism	
 • Withhold atezolizumab. • Initiate treatment with thyroid replacement hormone. • Monitor TSH weekly. • Consider patient referral to endocrinologist. • Resume atezolizumab when symptoms are controlled and thyroid function is improving.
Asymptomatic hyperthyroidism	
TSH ≥ 0.1 mU/L and < 0.5 mU/L:
 
 • Continue atezolizumab. • Monitor TSH every 4 weeks. 
TSH < 0.1 mU/L:
 
 • Follow guidelines for symptomatic hyperthyroidism.
Symptomatic hyperthyroidism	
 • Withhold atezolizumab. • Initiate treatment with anti-thyroid drug such as methimazole or carbimazole as needed. • Consider patient referral to endocrinologist. • Resume atezolizumab when symptoms are controlled and thyroid function is improving. • Permanently discontinue atezolizumab.
Symptomatic adrenal insufficiency, Grade 2–4	
 • Withhold atezolizumab for up to 12 weeks after event onset.^a • Refer patient to endocrinologist. • Perform appropriate imaging. • Initiate treatment with corticosteroids equivalent to 1–2 mg/kg/day IV methylprednisolone and convert to 1–2 mg/kg/day oral prednisone or equivalent upon improvement. • If event resolves to Grade 1 or better and patient is stable on replacement therapy, resume atezolizumab.^b • If event does not resolve to Grade 1 or better or patient is not stable on replacement therapy while withholding atezolizumab, permanently discontinue atezolizumab.
Hyperglycemia, Grade 1 or 2	
 • Continue atezolizumab.

Event	Management
	
 Investigate for diabetes. If patient has Type 1 diabetes, treat as a Grade 3 event. If patient does not have Type 1 diabetes, treat as per institutional guidelines. Monitor for glucose control.
Hyperglycemia, Grade 3 or 4	
 Withhold atezolizumab. Initiate treatment with insulin. Monitor for glucose control. Consider referral to endocrinologist, particularly if patient is deemed to have atezolizumab-induced diabetes; if so, obtain C-peptide level paired with glucose, autoantibody levels (e.g. GAD65, islet cell autoantibodies), and hemoglobin A1C level. If patient is found to have diabetic ketoacidosis or hyperglycemic hyperosmolar syndrome, treat as per institutional guidelines with appropriate management and laboratory values (e.g. anion gap, ketones, blood pH, etc.) reported. Resume atezolizumab when symptoms resolve and glucose levels are stable.
Hypophysitis (pan-hypopituitarism), Grade 2 or 3	
 Withhold atezolizumab for up to 12 weeks after event onset.^a Refer patient to endocrinologist. Perform brain MRI (pituitary protocol). Initiate treatment with corticosteroids equivalent to 1–2 mg/kg/day IV methylprednisolone and convert to 1–2 mg/kg/day oral prednisone or equivalent upon improvement. Initiate hormone replacement if clinically indicated. If event resolves to Grade 1 or better, resume atezolizumab.^b If event does not resolve to Grade 1 or better while withholding atezolizumab, permanently discontinue atezolizumab. For recurrent hypophysitis, treat as a Grade 4 event.
Hypophysitis (pan-hypopituitarism), Grade 4	
 Permanently discontinue atezolizumab. Refer patient to endocrinologist. Perform brain MRI (pituitary protocol). Initiate treatment with corticosteroids equivalent to 1–2 mg/kg/day IV methylprednisolone and convert to 1–2 mg/kg/day oral prednisone or equivalent upon improvement. Initiate hormone replacement if clinically indicated.

MRI = magnetic resonance imaging; TSH = thyroid-stimulating hormone.

^a Atezolizumab may be withheld for a longer period of time (*i.e.*, >12 weeks after event onset) to allow for corticosteroids (if initiated) to be reduced to the equivalent of ≤10 mg/day oral prednisone. The acceptable length of the extended period of time must be determined by the investigator.

^b If corticosteroids have been initiated, they must be tapered over ≥1 month to the equivalent of ≤10 mg/day oral prednisone before atezolizumab can be resumed.

Ocular events

An ophthalmologist should evaluate visual complaints (*e.g.*, uveitis, retinal events). Management guidelines for ocular events are provided in the table below.

Event	Management
Ocular event, Grade 1	
 Continue atezolizumab. Patient referral to ophthalmologist is strongly recommended. Initiate treatment with topical corticosteroid eye drops and topical immunosuppressive therapy. If symptoms persist, treat as a Grade 2 event.
Ocular event, Grade 2	
 Withhold atezolizumab for up to 12 weeks after event onset.^a Patient referral to ophthalmologist is strongly recommended. Initiate treatment with topical corticosteroid eye drops and topical immunosuppressive therapy. If event resolves to Grade 1 or better, resume atezolizumab.^b If event does not resolve to Grade 1 or better while withholding atezolizumab, permanently discontinue atezolizumab.
Ocular event, Grade 3 or 4	
 Permanently discontinue atezolizumab. Refer patient to ophthalmologist. Initiate treatment with corticosteroids equivalent to 1–2 mg/kg/day oral prednisone. If event resolves to Grade 1 or better, taper corticosteroids over ≥1 month.

^a Atezolizumab may be withheld for a longer period of time (*i.e.*, >12 weeks after event onset) to allow for corticosteroids (if initiated) to be reduced to the equivalent of ≤10 mg/day oral prednisone. The acceptable length of the extended period of time must be determined by the investigator.

^b If corticosteroids have been initiated, they must be tapered over ≥1 month to the equivalent of ≤10 mg/day oral prednisone before atezolizumab can be resumed.

Immune-mediated Myocarditis

Immune-mediated myocarditis has been associated with the administration of atezolizumab. Immune-mediated myocarditis should be suspected in any patient presenting with signs or symptoms suggestive of myocarditis, including, but not limited to, laboratory (*e.g.*, B-NP [B-Natriuretic Peptide]) or cardiac imaging abnormalities, dyspnea, chest pain, palpitations, fatigue, decreased exercise tolerance, or syncope.

Immune-mediated myocarditis needs to be distinguished from myocarditis resulting from infection (commonly viral, *e.g.*, in a patient who reports a recent history of gastrointestinal illness), ischemic events, underlying arrhythmias, exacerbation of preexisting cardiac conditions, or progression of malignancy. All patients with possible myocarditis should be urgently evaluated by performing cardiac enzyme assessment, an electrocardiogram (ECG), a chest X-ray, an echocardiogram, and a cardiac MRI as appropriate per institutional guidelines. A cardiologist should be consulted. An endomyocardial biopsy may be considered to enable a definitive

diagnosis and appropriate treatment, if clinically indicated.

Patients with signs and symptoms of myocarditis, in the absence of an identified alternate etiology, should be treated according to the guidelines in the table below.

Event	Management
Immune-related myocarditis, Grade 2	
 • Withhold atezolizumab for up to 12 weeks after event onset^a. • Refer patient to cardiologist. • Initiate treatment as per institutional guidelines and consider antiarrhythmic drugs, temporary pacemaker, ECMO, or VAD as appropriate. • Consider treatment with corticosteroids equivalent to 1–2 mg/kg/day IV methylprednisolone and convert to 1–2 mg/kg/day oral prednisone or equivalent upon improvement. • If symptoms resolve to below Grade 2 (i.e. patient is completely asymptomatic), resume atezolizumab.^b • If symptoms do not resolve to below Grade 2 while withholding atezolizumab, permanently discontinue atezolizumab.
Immune-related myocarditis, Grade 3-4	
 • Permanently discontinue atezolizumab. • Refer patient to cardiologist. • Initiate treatment as per institutional guidelines and consider antiarrhythmic drugs, temporary pacemaker, ECMO, or VAD as appropriate. • Initiate treatment with corticosteroids equivalent to 1–2 mg/kg/day IV methylprednisolone and convert to 1–2 mg/kg/day oral prednisone or equivalent upon improvement. • If event does not improve within 48 hours after initiating corticosteroids, consider adding an immunosuppressive agent. • If symptoms resolve to below Grade 2, taper corticosteroids over ≥1 month.

ECMO = extracorporeal membrane oxygenation; VAD = ventricular assist device.

^a Atezolizumab may be withheld for a longer period of time (*i.e.*, >12 weeks after event onset) to allow for corticosteroids (if initiated) to be reduced to the equivalent of ≤10 mg/day oral prednisone. The acceptable length of the extended period of time must be documented by the investigator.

^b If corticosteroids have been initiated, they must be tapered over ≥1 month to the equivalent of ≤10 mg/day oral prednisone before atezolizumab can be resumed.

Infusion-Related Reactions and Cytokine-Release Syndrome

No premedication is indicated for the administration of Cycle 1 of atezolizumab. However, patients who experience an infusion-related reaction (IRR) or cytokine-release syndrome (CRS) with atezolizumab may receive premedication with antihistamines, antipyretics, and/or analgesics (*e.g.*, acetaminophen) for subsequent infusions. Metamizole (dipyrone) is prohibited in treating atezolizumab-associated IRRs because of its potential for causing agranulocytosis.

IRRs are known to occur with the administration of monoclonal antibodies and have been

reported with atezolizumab. These reactions, which are thought to be due to release of cytokines and/or other chemical mediators, occur within 24 hours of atezolizumab administration and are generally mild to moderate in severity.

CRS is defined as a supraphysiologic response following administration of any immune therapy that results in activation or engagement of endogenous or infused T cells and/or other immune effector cells. Symptoms can be progressive, always include fever at the onset, and may include hypotension, capillary leak (hypoxia), and end-organ dysfunction (Lee *et al.*, 2019). CRS has been well documented with chimeric antigen receptor T-cell therapies and bispecific T-cell engager antibody therapies but has also been reported with immunotherapies that target PD-1 or PD-L1 (Rotz *et al.*, 2017; Adashek and Feldman 2019) including atezolizumab.

There may be significant overlap in signs and symptoms of IRRs and CRS, and in recognition of the challenges in clinically distinguishing between the two, consolidated guidelines for medical management of IRRs and CRS are provided in the table below.

Management Guidelines for Infusion-Related Reactions and Cytokine-Release Syndrome

Event	Management
Grade 1 ^a Fever ^b with or without constitutional symptoms	
 • Immediately interrupt infusion. • Upon symptom resolution, wait 30 minutes and then restart infusion at half the rate being given at the time of event onset. • If the infusion is tolerated at the reduced rate for 30 minutes, the infusion rate may be increased to the original rate. • If symptoms recur, discontinue infusion of this dose. • Administer symptomatic treatment,^c including maintenance of IV fluids for hydration. • In case of rapid decline or prolonged CRS (> 2 days) or in patients with significant symptoms and/or comorbidities, consider managing as per Grade 2. • For subsequent infusions, consider administration of oral premedication with antihistamines, anti-pyretics, and/or analgesics, and monitor closely for IRRs and/or CRS.
Grade 2 ^a Fever ^b with hypotension not requiring vasopressors and/or Hypoxia requiring low-flow oxygen ^d by nasal cannula or blow-by	
 • Immediately interrupt atezolizumab infusion. • Upon symptom resolution, wait for 30 minutes and then restart infusion at half the rate being given at the time of event onset. • If symptoms recur, discontinue infusion of this dose. • Administer symptomatic treatment.^c • For hypotension, administer IV fluid bolus as needed. • Monitor cardiopulmonary and other organ function closely (in the ICU, if appropriate). Administer IV fluids as clinically indicated and manage constitutional symptoms and organ toxicities as per institutional practice. • Rule out other inflammatory conditions that can mimic CRS (e.g., sepsis). If no improvement within 24 hours, initiate workup and assess for signs and symptoms of HLH or MAS.

	
 ● Consider IV corticosteroids (e.g., methylprednisolone 2 mg/kg/day or dexamethasone 10 mg every 6 hours). ● Consider anti-cytokine therapy.^e ● Consider hospitalization until complete resolution of symptoms. If no improvement within 24 hours, manage as per Grade 3, that is, hospitalize patient (monitoring in the ICU is recommended), permanently discontinue atezolizumab. ● If symptoms resolve to Grade 1 or better for 3 consecutive days, the next dose of atezolizumab may be administered. For subsequent infusions, consider administration of oral premedication with antihistamines, anti-pyretics, and/or analgesics and monitor closely for IRRs and/or CRS. ● If symptoms do not resolve to Grade 1 or better for 3 consecutive days, contact the Principal Investigator.
